Prostate Contrast MRI	X (if randomised to focal therapy and no contrast given during diagnostic scan – to have prior to visit 2)							
Prostate mpMRI				X (focal therapy arms)				
Biopsy (optional)				X (focal therapy arms)				
Treatment		X (these vary in length)		,				X (focal therapy arms – a second treatment will be permitted for a histologically confirmed recurrent residual or new out-of-field disease)
Clinical assessment (optional, only if required)			X	Х	X	X	X	
PROMS questionnaires	Х		Х	Х		Х		X (every 12 months, at 24, 36, 48 and 60 months visits)
Review/ reporting of patient AEs/SAEs		X	Х	Х	X	X	Х	X
Blood and urine tests including those for	Х		Х	Х				Х

Short Title:	Protocol No:	Sponsor:	Version: 5.0
IP4 - CHRONOS	19CX5006	Imperial College London	Date:
			13 th July 2022

biobanking (optional)				

Time window for each visit will be +/- 4 weeks

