- As there is no defined time-point for a PSA nadir value following FT the PSA value at 12-months post randomisation in patients with a negative MRI will be used. Following this if there are any two further consecutive rises in PSA at least 3 months apart, with no influencing factors at the time (e.g., urinary tract infection, instrumentation/procedures, biopsies, catheterisation), a for-cause mpMRI with or without biopsies can be carried out at the discretion of the treating clinician. The Focal Therapy Sub-Group should be informed of this and a review of the for-cause mpMRI findings prior to biopsy should be carried out. Clinically significant prostate cancer in-field that is suitable for further FT should be offered to patients as a routine. Radical therapy should be only recommended to patients in instances where further FT is not suitable. Such situations should only occur after the Focal Therapy Subgroup has reviewed the case as expertise for such decisions may not reside in the local centre.
- In CHRONOS A, a second treatment either in-field or out-of-field will not be classified as failure and is part of the overall focal therapy intervention. In patients who undergo a second treatment of FT the nadir value will be defined at the 12-month time point after the second treatment, provided mpMRI and biopsy targeted at treated area(s) are negative for clinically significant prostate cancer.

Radiotherapy/ Brachytherapy

 In patients where there is suspected PSA relapse but the international definition of biochemical failure (PSA nadir plus 2.0ng/ml) has not been reached, evaluation should include a for-cause mpMRI and biopsy if required. Staging scans should be done as

Short Title: IP4 - CHRONOS	Protocol No: 19CX5006	Sponsor: Imperial College London	Version: 5.0 Date: 13 th July 2022
			10 daily 2022

per local practice. Where salvage local or systemic therapy is given, this will be regarded as PFS event.

Surgery

- Adjuvant or salvage radiotherapy will be regarded as a PFS event and will be determined based on histological findings and PSA kinetics even if the biochemical failure definition is not reached (PSA >/=0.2ng/ml). Staging scans should be done as per local practice.
- Biochemical failure following radical therapy as internationally defined, even if salvage therapy is not given, will be counted as an event for PFS/FFS analyses.

Collection of postcodes

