In order to get an area-based estimate of deprivation, the participants' postcodes will be converted into an Index of Multiple Deprivation (IMD) score. The IMD is the established index of deprivation for England Wales and has been adopted widely in studies across local and national government. Postcodes will not be stored in the InForm Database only IMD rank, which is based on detailed ward-level index of deprivation based on severe separate domains.

Prostate Specific Antigen (PSA)

Blood sample for PSA can be collected during a scheduled hospital visit or at a hospital local to the patient or at a community/primary care facility, whichever is more convenient for the patient provided the result is available to the research team.

Patient reported outcome measures (PROMS)

PROMS questionnaires can be completed or returned during a scheduled hospital visit or via post/electronic communication.

Further follow-up imaging

Follow-up imaging will not be protocol led, except after focal therapy at the 12 month post focal therapy time-point) but we recommend imaging to take place when there is suspicion of progression such as patients with a rising PSA (biochemical failure). The appropriate imaging will be chosen as per the local hospital resources and policies. We envisage that the majority will perform a combination of a prostate MRI, nuclear medicine bone scan, PET-CT/MRI, Whole body MRI or CT chest/abdomen/pelvis.

Further follow-up biopsies

Some patients will undergo further biopsies if there is a need to confirm disease progression after the 12 month follow-up visit following focal therapy.

Further interventions

Some patients will also undergo secondary non-cancer related procedures to manage adverse events from the therapy such as, but not limited to, transurethral resection of prostate, bladder neck incision, urethral dilatation, optical urethrotomy, male-sling or other continence procedures as well as penile implant surgery for impotence. Endoscopic tests or interventions of the lower bowel may also be required. These rates of interventions will be collected.

Future follow-up

Patients will be consented for their names to be linked to national registries for survival information such as NHS Information Centre/Office of National Statistics (ONS) in England/Wales and General Register Office in Scotland, Hospital Episode Statistics (HES).

Protocol No: 19CX5006 v5.0 13th July 2022

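### CHRONOS-B: the for-cause mpMRI review that precedes biopsy is not required to be masked to arm, although a repeat focal session is the commonest expected FFS failure and is decided open label

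*Protocol*

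**What the plan says.** **Endpoint and blinding.** Protocol 2.5 counts one further focal session as an FFS failure in CHRONOS-B, alongside salvage therapy, metastases and prostate cancer death. Section 5.8 repeats that a second in-field session, or a first out-of-field one, is a failure. Neither section makes the event depend on histology or adjudication. Sections 3.1 and 5.4 make the trial open label for physician and patient.

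**The for-cause route (5.9).** The reference PSA is defined so: "the PSA value at 12-months post randomisation in patients with a negative MRI will be used". The trigger is "any two further consecutive rises in PSA at least 3 months apart, with no influencing factors at the time", after which "a for-cause mpMRI with or without biopsies can be carried out at the discretion of the treating clinician". Then: "The Focal Therapy Sub-Group should be informed of this and a review of the for-cause mpMRI findings prior to biopsy should be carried out". The text does not name who carries out the review, and does not mention masking.

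**Treatment after the work-up.** "Clinically significant prostate cancer in-field that is suitable for further FT should be offered to patients as a routine". Radical therapy is for cases where further focal therapy is unsuitable, and "Such situations should only occur after the Focal Therapy Subgroup has reviewed the case". More generally, 5.9 says that "we recommend imaging to take place when there is suspicion of progression".

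**Histology.** The visit schedule in 5.7 says that "a second treatment will be permitted for a histologically confirmed recurrent residual or new out-of-field disease". The 12-month biopsy is optional. Section 9.7 has all deviations reported through the eCRF.

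**The concern.** Whether a man has a repeat session depends on a chain of judgements: whether to scan, whether the scan justifies biopsy, and whether the result justifies treatment. Everyone in that chain may know whether he received finasteride, bicalutamide or neither. If that knowledge changes how readily the same findings lead to biopsy, the FFS hazard ratio moves without any true drug effect, and the Cox analysis in 8.3 cannot tell the two apart.

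The shift could go either way. More readiness to re-treat control men would favour a drug; more readiness to re-treat drug-arm men would count against it. The first risks adopting an inactive drug, the second dropping an active one.

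Most links in the chain cannot be masked in an open-label surgical trial. The pre-biopsy review of the for-cause scan can be, and the protocol already provides for it. The point concerns the main-stage FFS comparison, not the pilot's feasibility endpoints.

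**Working it through.** **1. Is a repeat session the commonest expected failure?** Protocol 1.1 gives redo rates of about 20-30%, salvage radical or systemic therapy in 10%, metastases in 3% and cancer-specific survival of 100%, over a 5-year median follow-up. The order is clear, although the protocol does not itself break FFS down by component. Taking 20% redo and 10% salvage, with no man having both (assumption), gives 30%. That matches the 30% failures by 5 years in 8.1.2. The repeat share is then 20/30 = 2/3, or 80 of 120 control events.

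**2. The plan's own event number.** Inputs from 8.1.2 and Table 2: HR 0.67, one-sided alpha 0.025, power 85%, equal allocation.
- Ratio of drug-arm to control events: (1 − 0.7^0.67)/0.3 = 0.709.
- Control events: [1.960·√2 + 1.036·√(1 + 1/0.709)]² / (ln 0.67)² = (2.772 + 1.609)² / 0.1604 = 119.7, against 120 stated.

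The design figure reproduces and is not in dispute.

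**3. Illustration of a shift, no true effect.** Let s be the share of control failures that are repeat sessions by the for-cause route. Let control men be re-treated k times as often as drug-arm men for the same findings on that route.
- x = s(k − 1); apparent HR = 1/(1 + x).
- SE = √(1/120 + 1/(120·HR)).
- One-sided error = Φ(−1.96 − ln(HR)/SE).
- Extra control events among the 120 = 120·x/(1 + x).

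The documents do not say what fraction of repeat sessions follows the for-cause route rather than the scheduled 12-month mpMRI. A half and a quarter are assumptions, giving s = 1/3 and 1/6. The values of k are also assumptions.

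| For-cause fraction | s | k | x | Apparent HR | SE | Error | Extra events |
|---|---|---|---|---|---|---|---|
| half | 1/3 | 1.10 | 0.033 | 0.968 | 0.130 | 4.4% | 3.9 |
| half | 1/3 | 1.20 | 0.067 | 0.938 | 0.131 | 7.1% | 7.5 |
| quarter | 1/6 | 1.10 | 0.017 | 0.984 | 0.130 | 3.3% | 2.0 |
| quarter | 1/6 | 1.20 | 0.033 | 0.968 | 0.130 | 4.4% | 3.9 |

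First row: ln(0.968) = −0.0328; 0.0328/0.1302 = 0.252; Φ(−1.96 + 0.252) = Φ(−1.708) = 0.044.

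**4. The opposite direction.** With true HR 0.67 and drug-arm repeats raised by a proportion r on this route, apparent HR = 0.67(1 + s·r). Power uses the variances of step 2. For s = 1/3, r = 10% gives HR 0.692 and power 79%; r = 20% gives HR 0.715 and power 72%, against 85% planned.

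Steps 3 and 4 are single-stage approximations at the final analysis. They ignore the activity hurdle at HR 0.974.

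**The case against.** **The open-label choice is declared, and safeguards exist.** This stands. There is a PSA trigger, notification of the Sub-Group, review of the scan before biopsy, a routine offer of further focal therapy for suitable significant in-field disease, and a histology rule in 5.7. None of them requires masking, and reading a scan can be masked even where treatment cannot.

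**Applying an excess to every repeat session overstates what masking can mend.** This stands. With s = 2/3, excesses of 10% and 20% would give 7.1% and 15.4%. A reader might take those as the size of the problem. The for-cause route begins only after the 12-month reference PSA in men with a negative MRI, so earlier re-treatment lies outside it. Even the smaller figures above rest on assumed excesses.

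**A reader might infer that the plan lets unconfirmed repeat sessions drive FFS.** The documents do not support that. Section 5.7 permits a second treatment for histologically confirmed disease. The optional biopsy is the 12-month one, and the with-or-without wording belongs to the for-cause work-up; neither waives confirmation before re-treatment. An unconfirmed session would be a reportable deviation, and nothing suggests how often it would happen. Section 2.6 also plans rates of positive biopsy and of second or third focal sessions, which compared by arm give a partial check.

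**Masking may be specified elsewhere.** Possible. The biopsy and focal therapy SOPs are separate and not in the documents. If they cover it, a cross-reference in 5.9 closes the point.

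**Conclusion.** The point holds as a cheap improvement, not as an error in the plan. CHRONOS-B is open label, a repeat session is a failure without further condition, and the for-cause mpMRI review is not required to be masked to arm.

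The documents give neither the size nor the direction of any bias. Under the stated assumptions (repeat sessions two-thirds of control failures, a quarter to a half of them by the for-cause route, a 10-20% excess in control men), the one-sided 2.5% error becomes about 3.3% to 7.1%. An excess in drug-arm men would cost power instead.

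It does not follow that the FFS comparison is biased, or that masking this review would make it safe. Nor is the lack of a supportive FFS analysis in the SAP an error: that SAP covers the feasibility stage only.

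**What to change.** Before the main stage, amend Protocol 5.9 for CHRONOS-B:

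- The Focal Therapy Sub-Group carries out the for-cause mpMRI review without knowledge of arm.
- Allocation, drug dates and randomisation date are removed from what it sees. The randomisation date matters because drug-arm men have focal therapy at least 12 weeks after randomisation, so the gap to treatment could disclose the arm.
- The reference PSA is supplied, labelled as such, with later PSAs given as months after it. The rule of two rises at least 3 months apart can then still be applied.
- Unmasking is allowed on clinical request.

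**Cost.** Some redaction work; no new procedure for patients, and no change to the endpoint or sample size. Protection is partial. Other dates or findings may hint at the arm, and masking does not reach the decision to scan, re-treatment after the scheduled 12-month mpMRI, or the treating clinician's final decision.

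**Optional and secondary.** The main-stage SAP could add a supportive FFS analysis that counts only histologically confirmed repeat sessions, with the other components unchanged. It would matter only if unconfirmed sessions occur as deviations, and it would remain open to differential biopsy between arms.

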5.10 Laboratory Evaluations

Blood test: PSA will be measured as per standard care and using local laboratory processes and assays. Centralised measure of PSA will not be used. No additional haematology or biochemistry tests will be mandated by the trial. It is envisaged that standard of care haematological and biochemical tests will be ordered by the treating clinician to monitor for pre-assessment requirements for anaesthetic fitness or for assessing treatment related toxicity.

Urinalysis: No additional urinalysis test will be mandated by the trial.

Exploratory / Research samples: Research samples including tissue, blood and urine will be collected and stored as per the details below and will be taken at each of the predefined time points. Protocols for analysis will be added as substantial amendments. Patients will be informed that exploratory studies will take place and consent will be taken for these at initial recruitment. The exact nature of these studies will not be disclosed and further consent in the future will not be asked for prior to proceeding. The following statements have been added to the PIS:

"All samples taken will be transferred to the Imperial College Healthcare Tissue Bank or partner biobank in the UK and will be used for histological, genomic and epigenetic analysis and for ethically approved future studies by our team or other scientists interested in prostate cancer research. Samples will not have any personal information written on them. Researchers will not be able to identify you from your samples."

Short Title: IP4 - CHRONOS	Protocol No: 19CX5006	Sponsor: Imperial College London	Version: 5.0 Date: 13 th July 2022
			10 daily 2022

The following statement has been added to the Informed Consent Form:

"I give permission for any blood, urine and tissue samples, as described in the information sheet, to be used for this and for further ethically approved research in the field of prostate cancer research. I give permission for my samples and data from any scans to be sent and be utilised in research both in the UK and worldwide. All material will be anonymous and I will not be identifiable. I understand that I will not be asked again for permission to run these additional research tests and I may also not be informed of the results."

Sample storage and analysis

All additional research samples that are taken will be processed, handled and stored at the Imperial College Health Care Tissue Bank (ICHTB) or partner UK biobank as per their standard operating procedures (SOPs). Transfer of biobanked samples may be needed to local, national and international laboratories and this will be in accordance with the ICHTB or our partner laboratory SOPs both within and outside of the UK.

The standard care urine samples taken as part of routine clinical care will be stored for 7 days post analysis and then auto disposed in tiger stripe (offensive waste) bag as per the Trust Clinical Waste Management Policy.

Urine samples may be collected and stored for biobanking and may in future undergo further analysis if new biomarkers are discovered that may be of clinical use in diagnosing prostate cancer (optional consent). Urine samples for biobanking will be stored in -80' C freezers within approved biobank facilities at Imperial College Healthcare Tissue Bank or a partner UK biobank for a period of 10 years.

Blood for standard care tests in clinical care will be via peripheral venepuncture and placed in a plastic tube containing SST (serum separating tube). This will be processed in a local laboratory. The blood samples will be stored for 4 days post analysis and then auto disposed to bio-bins and incinerated off site according to the Trust Clinical Waste Management Policy.

Additional blood samples may be collected and stored for biobanking and in future may undergo further analysis if new biomarkers are discovered that may be of clinical use in diagnosing prostate cancer (optional consent). Blood samples for biobanking will be stored in -80' C freezers within approved biobank facilities at Imperial College Healthcare Tissue Bank or partner UK biobank for a period of 10 years. At the end of the study if there are any samples left these will be held under the Imperial College Healthcare Tissue Bank (ICHTB) HTA licence 12275 and any further use of the samples will be approved via an ethics approval committee within the ICHTB.

Blood and urine samples taken for biomarkers will be collected at the local treating hospital site and transferred to the aforementioned biobank facilities for storage.

Samples may also be transported for tests that can only be run outside of the UK. If needed ethics approval will be sought for any such tests.

Imaging scan data

Short Title: IP4 - CHRONOS	Protocol No: 19CX5006	Sponsor: Imperial College London	Version: 5.0 Date: 13 th July 2022
			13 July 2022

Imaging scans are performed as part of this study. We will also ask for optional consent from patients to store and use their scan data in future research to see if new ways of looking at these scans can detect cancer better in the future.

Health Status

At the screening visit, patients will also be asked to give optional consent for identifiable data to be linked with the national databases (ONS and HES database). The identifiable fields (NHS number) required for linkage will be encrypted using a one-way encryption algorithm. We will ask patients if they are happy to give consent for their health status to be followed up over time. This will be done by linking your name and NHS number with records held by the NHS and maintained by the NHS Information Centre and the NHS Central Register, or any applicable NHS information system. This will allow us to track what happens after the study finishes and observe if anyone gets cancer in future and about the type of cancer and the treatment they have had.

We will also ask patients whether or not they give permission to be contacted by a member of the study research team within 10 years of signing their consent form, after the study has ended to assess their willingness to complete a questionnaire about their health status (including details of any other tests and treatment they have had since the study) and quality of life. If the patient decides to take part a member of the research team will check the hospital/GP records to ensure patient status before sending this request to the patient's home address.

As prostate cancer is often a slow-growing disease which may not progress for many years we will also ask patients if they are happy to keep personal data be stored or accessed for an additional 10 years on the NHSCR (National Health Service Care Register). This is an optional part of consent.

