 - If a Likert or PIRADS score 3,4 or 5 mpMRI lesion is present in an area outside of the treatment field with a negative biopsy for cancer then pathology must be reviewed and confirm the presence of inflammation or atrophy if the patient is to undergo focal therapy*
- Radiological stage T2b/T3a will require central review regarding suitability for focal therapy.
- Index tumour volume, as seen on mpMRI if carried out, will be restricted to 50% of one lobe for either unilateral or bilateral ablation, patients with tumour volume >/=50% of one lobe will require central review prior to enrolment. Final decisions on suitability of focal therapy will lie with the trial central review in these cases.
- Age at least 18 years of age
- Participants must be fit to undergo all procedures listed in the protocol as judged by clinical team

*A biopsy of a suspicious mpMRI area may miss underlying cancer due to targeting error. However, if there is an alternative diagnosis for the changes on mpMRI such as inflammation or atrophy then this risk is reduced.

**This is to ensure that inappropriately large tumours are not being treated with focal therapy.

Exclusion criteria

- Previous or current LHRH agonist or LHRH antagonist or anti-androgen use in CHRONOS-B.
- Patients already established on a 5 alpha-reductase inhibitor (finasteride or dutasteride) who wish to go into CHRONOS-B will need to discontinue this for at least 6 months prior to randomisation. (NB: testosterone supplementation is permitted)
- Previous treatment for prostate cancer
- Life expectancy is likely to be less than 10 years
- Unable to give informed consent

Short Title: IP4 - CHRONOS	Protocol No: 19CX5006	Sponsor: Imperial College London	Version: 5.0 Date: 13 th July 2022
			10 daily 2022

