5.7 Visit Schedule

The design and number of visits mirror the standard of care pathway for patients undergoing either focal therapy or radical therapy, so that additional patient burden is minimal. Prior to enrolment, all patients will have undergone a Prostate Specific Antigen (PSA) blood test, a diagnostic prostate MRI and prostate biopsies. A standard of care (SOC) multi-disciplinary team case review will precede any discussion with the patient on all suitable treatment options and trial suitability. After an MDT discussion confirming suitability for FT and/or radical therapy has taken place, a patient information sheet (PIS) explaining the study will be provided, after which patients will be given a minimum of 24 hours to consider taking part. We aim for consent to be taken during a SOC appointment, or an additional consultation via phone, or in person. Randomisation will take place during the visit in which consent is taken along with any required neoadjuvant therapy, as allocated via randomisation, to be prescribed and within 24 hours of receiving the prescription. Time from randomisation will be used to define progression free survival and failure free survival. The end of treatment is defined as the final part of any intervention. For radiotherapy, this is the final radiation fraction completed and for prostatectomy and focal therapy the point at which the catheter is removed. Therefore, the follow-up visits noted below will start from these time-points, which will define the date of first follow-up visit (visit 2).

Protocol No: 19CX5006 v5.0 13th July 2022

IP4 - CHRONOS 19CX5006 Imperial College London Date: 13 th July 2022

Visit Schedule:

	Screening & Consent	Visit						
Visit	1	2	3	4	5	6	7	6 monthly visits until last visit 60 months after visit 2
Months		These below specify the months after the completion of each treatment in each arm						
		0	3	12	18	24	30	31-60. Visits 4 onwards can be telephone consultations in order t note clinical outcomes although MRI scans and biopsies where done will require physical visits to the hospital
Informed Consent and enrolment into either CHRONOS A or CHRONOS B	Х							
Inclusion & exclusion criteria checked, including concomitant medication review	Х							
Randomisation	Х							
Prescription of neo- adjuvant therapy	X (if randomised to such arm)							Within 24hrs of randomisation
PSA blood test	Such anny		Х	Х	Х	Х	Х	X (6 monthly)

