6.6 Drug Interactions/ Precautions/ Contraindications

Finasteride

Interactions:

No drug interactions of clinical importance have been identified.

Precautions:

Obstructive uropathy

Advised for patients to use effective contraception during treatment due to risk of morphological changes in spermatozoa

Contraindications:

Hypersensitivity reaction to 5-alpha reductase inhibitors

Bicalutamide

Interactions:

Severe: none identified Moderate: Lomitapide* Mild: none identified

*theoretical

Precautions:

Risk of photosensitivity- advised to avoid exposure to UV light and sunlight Monitoring of liver function tests required- accumulation may occur in moderate to severe hepatic impairment

Protocol No: 19CX5006 v5.0 13th July 2022

Short Title: IP4 - CHRONOS	Protocol No: 19CX5006	Sponsor: Imperial College London	Version: 5.0 Date: 13 th July 2022
			13 July 2022

Advised for patients to use effective contraception during treatment due to risk of morphological changes in spermatozoa

No dose adjustment is required in the elderly patients or patients with renal impairment

Contraindications:

Hypersensitivity to anti-androgen therapy

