6.8 Dose Modification for Toxicity

Finasteride

No dose changes are recommended for renal or hepatic impairment

Bicalutamide

No dose changes are recommended for renal impairment Advised caution in patients with moderate- severe hepatic impairment

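### Arm 3 liver-function monitoring is called required but is not assured by the schedule, and on the protocol's own Visit 2 definition no adverse-event review is scheduled while men in Arms 2 and 3 are on drug

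*Protocol*

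**What the plan says.** **Liver tests.** Among the bicalutamide precautions, Protocol 6.6 states: "Monitoring of liver function tests required- accumulation may occur in moderate to severe hepatic impairment". It gives no timing, threshold or action. Protocol 6.8 adds: "Advised caution in patients with moderate- severe hepatic impairment". Protocol 5.10 states: "No additional haematology or biochemistry tests will be mandated by the trial". Its next sentence envisages standard-care bloods "ordered by the treating clinician to monitor for pre-assessment requirements for anaesthetic fitness or for assessing treatment related toxicity". In the 5.7 table the only blood rows are PSA and an optional row, "Blood and urine tests including those for" biobanking, marked at Visits 1, 3, 4 and later. The nearest eligibility item in 4.1 is "Participants must be fit to undergo all procedures listed in the protocol as judged by clinical team".

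**Adverse-event review.** Protocol 5.7 defines the end of treatment as "for prostatectomy and focal therapy the point at which the catheter is removed" and dates Visit 2 from that point. The AE/SAE row in the same table is blank at Visit 1 and marked from Visit 2. Under 6.4 the drug is dispensed within a day of randomisation and taken for 12 weeks before focal therapy; 6.1 makes 12 weeks the minimum.

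**The concern.** Bicalutamide is an investigational product in this trial, and the CHRONOS-B control arm is focal therapy alone, so the control pathway brings no drug monitoring with it. If testing is left to each site, three things follow.

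- An Arm 3 man may start and finish the drug without a liver test, including a man in the group for whom 6.6 warns of accumulation.
- Protocol 7.2 makes clinically important abnormal results in Arms 2 and 3 adverse events, so those counts partly reflect how often each site tests.
- Without a scheduled contact on drug, non-serious events reach the data by unscheduled routes or by recall some 12 weeks or more after the drug began. A man who stops the drug and never has focal therapy has no dated review.

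Adverse events carry weight in this design. Protocol 1.2.1 justifies the multi-arm design partly by early stopping of arms with too many of them, 11.4 allows a harmful arm to be closed, and SAP 8.3 lists their occurrence among the primary end point variables.

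**Working it through.** The plan gives no figure to reproduce. The check sets the relevant texts side by side and then counts the men affected.

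**Is a liver test assured in Arm 3?**

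1. Requirement: 6.6 says monitoring is required.
2. Trial mandate: 5.10 adds no biochemistry.
3. Standard care: 5.10 expects the clinician to order bloods for two purposes. Anaesthetic work-up need not give a pre-drug baseline. Toxicity assessment is at the clinician's discretion and undated.
4. Schedule: 5.7 names no liver test. Its general blood row is optional and, on the protocol's visit definitions, has no mark between drug start and focal therapy.
5. Eligibility: 4.1 has no hepatic criterion and no baseline liver test.
6. Abnormal results: 7.2 says how a result is handled once found. It orders no test.

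Steps 2 to 6 contain no instruction that would make step 1 happen. Nor do they forbid it.

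**Is an adverse-event review scheduled on drug?**

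1. Drug start: within 24 hours of randomisation, at Visit 1 (6.4, 5.7).
2. Course length: 12 weeks × 7 = 84 days at least, for a man who completes it.
3. Focal therapy, then catheter removal, which dates Visit 2 (5.7).
4. First mark in the AE/SAE row: Visit 2.

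On that sequence, no mark falls during the course. The patient-reported questionnaires do not fill the gap: in the pilot they are at screening and 3 months (SAP 9.4), the latter counted from the end of treatment.

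**Does the SAP place Visit 2 elsewhere?** Its labels differ.

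- SAP 9.3 calls Visit 2 the treatment visit, and SAP 8.3 puts blister-pack return among Visit 2 data. Both fit the protocol, since 6.4 asks for packs back at the focal therapy visit.
- SAP 5.1 records receipt of the drug at Visit 2 and pack return at Visit 3, and the footnote to Table 2.9 puts CHRONOS-B treatment data at Visit 3. These suggest a Visit 2 tied to the drug.

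**Men affected** (Protocol 3.2)

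- Liver tests: 20 pilot men in Arm 3.
- Adverse-event review: 20 + 20 = 40 of 60 pilot men.
- Main stage, if funded: 400 in Arm 3 for liver tests; 2 × 400 = 800 in both drug arms for review.

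**The case against.** **The two liver statements can both hold.** A reader might infer that 6.6 and 5.10 contradict each other. The documents do not support that. 5.10 says only that the trial mandates nothing additional, and it then gives toxicity bloods to the treating clinician. Section 6.6 is a precautions list and does not say who orders the test. Section 6.1 notes that both drugs are used in standard practice, and 7.2 presupposes some testing, since important abnormal tests are to be repeated. What stands is that the requirement has no owner, no date and no place in the schedule.

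**6.6 may be narrower than it looks.** The sentence links monitoring to accumulation in hepatic impairment and may be meant only for those men. That is a fair reading. It reduces the number affected but leaves the question of how those men are found.

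**The plan has some screening.** It would be too strong to say that nothing could pick up a man with liver disease. There is multidisciplinary review, a medication check at Visit 1, a judgement of fitness and an exclusion for life expectancy under 10 years, and 6.11 lets the investigator stop the drug. None of these is a liver test.

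**Adverse events are captured without a visit.** A reader might infer that events on drug go unrecorded. They do not. SAP 9.3 has adverse events recorded on eCRFs throughout the trial, and the Table 2.17 listing has columns for relationship to the trial drug and action taken with it. Protocol 7.3 requires serious events within 24 hours, 6.4 has compliance reported regularly, and SAP Table 2.12 includes adverse events among reasons for withdrawal. This objection succeeds against any claim about capture. It does not supply a scheduled contact. The 24-hour rule covers serious events only, and 7.3 exempts expected systemic toxicity from SAE reporting, although it is still collected.

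**The pilot's main estimates are untouched.** Recruitment, randomisation and compliance rates do not depend on this, and the safety analysis is descriptive. That is correct. The case for change rests on patient safety and comparable adverse-event data.

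**Conclusion.** The point holds in two limited parts, of unequal strength.

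**Liver tests (firmer).** Monitoring that 6.6 calls required is not assured by 5.10, 5.7 or 4.1. It concerns all 20 pilot Arm 3 men or, on the narrow reading, the subset with hepatic impairment, whom no required test would identify. This does not depend on how Visit 2 is read, because no visit names a liver test.

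**Adverse-event review (conditional).** On the protocol's definition of Visit 2, 40 of 60 pilot men have no scheduled review during at least 84 days on drug. The gap is in scheduled contact only, and it narrows if Visit 2 is in practice a drug visit, as SAP 5.1 suggests.

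The documents give no frequency for hepatic impairment, or for men who stop the drug and have no focal therapy, so no number of harmed or missed men can be stated. How much liver testing matters for 12 weeks at 50 mg rests on product information that is not in the documents. The change is still worth making, because it is cheap and carries out what the protocol itself calls for.

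**What to change.** 1. In 5.10, except the Arm 3 liver tests that 6.6 requires. Add a row to 5.7 with a baseline test and on-drug timing. The sponsor should set that timing, and the action on an abnormal result, from the product information. If the sponsor limits 6.6 to men with hepatic impairment, keep the baseline test so that they can be identified.
2. Start the AE/SAE row in 5.7 at randomisation. Add one remote adverse-event check at the end or discontinuation of drug for every Arm 2 and Arm 3 man, whether or not he has focal therapy.
3. As housekeeping, align the SAP's Visit 2 and Visit 3 labels for CHRONOS-B with the protocol.

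**Cost.** A protocol amendment with ethics and regulatory approval and notification of the HRA and sites (9.4, 9.5). About 40 short remote contacts in the pilot, or 800 in all if the main stage is funded; 5.9 already permits remote data collection. For liver tests, assuming one baseline and one to three on drug, 20 × 2 = 40 to 20 × 4 = 80 in the pilot, some of which standard care may already supply.
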